#### 3.6.3 Additional safety assessments

#### 3.6.3.1 Laboratory variables, vital signs and electrocardiograms (ECGs)

The following laboratory variables, vital signs and electrocardiogram (ECG) variables will be analyzed. They will be converted into standard international units and conventional units, if applicable.

- Hematology:
  - Red blood cells and platelet: red blood cell count, platelet count, hemoglobin, hematocrit
  - White blood cells: white blood cell count, neutrophils, lymphocytes, monocytes, basophils, eosinophils
- Clinical chemistry:
  - Metabolism: glucose, total protein, albumin, creatine phosphokinase, lipase
  - Electrolytes: sodium, potassium, chloride, calcium, bicarbonate
  - Renal function: creatinine, creatinine clearance, blood urea nitrogen. (Creatinine clearance will be derived with the equation of Cockcroft and Gault using weight assessed at the same visit as creatinine.)
  - Liver function: alanine aminotransferase (ALT), aspartate aminotransferase (AST), alkaline phosphatase, total and direct bilirubin
- Urinalysis for quantitative analysis: specific gravity, pH
- Vital signs: heart rate, systolic and diastolic blood pressure, weight, temperature
- ECG variables: heart rate, PR, QRS, QT, and corrected QTcF (according to Fridericia). In case the ECG machine does not automatically calculate QTcF, manual calculation using nomogram or automatic website calculator is acceptable.

For laboratory data reported as  $\langle xx \text{ or } \rangle yy$ , a numeric value of xx/2 or yy, respectively, will be used for quantitative analysis.

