1.3 SCHEDULE OF ACTIVITIES (SOA)

Procedure	Screening ^a	Randomization/ start of IMP						Το Υ	ear 2 (M24) ^k	b								4	From M27 to EOS ⁰	Only for participants who prematurely discontinue IMP	For all participants	Only for participants who completed treatment EOS but do not enter LTS ^c
Visit (a window of ±7 days is allowed for all visits after D1)	D-28 to D-1	D1	M0.5 (W2) M0.75 (W3)	M1(W4) ^d	M1.25 (W5) M1.5 (W6) M1.75 (W7)	M2 (W8) ^d	M2.25 (W9) M2.5 (W10) M2.75 (W11)	М3	M4, M5 ^d	М6	M7 M8	М9	M10 M11	M12	M15	M18	M21	M24	Quarterly visits (M27, M30, M33, M36, M39, M42, M45, M48)	Semi- annual visits (M30, M36, M42, M48)	pEOT ^e	EOS "Common study end date" visit ^f	Follow-up visit (4 weeks)
Visit Number	V1	V2		V3		V4		V5	V6, V7	V8		V9		V10	V11	V12	V13	V14	V15, V16, V17, V18, V19, V20, V21, V22	V16, V18, V20, V22	pEOT ^e	EOS	FUV
Informed consent	Х																						
Demography	Х																						
Inclusion/exclusion criteria	х	х																					
Medical/surgical history	х																						
Prior/concomitant medications ^g	+ ==												======										≯
Randomization		Х																					
IRT contact	Х	Х						Х		Х		Х		Х	Х	Х	Х	Х	Х	Х	Х	Х	Х

Procedure	Screening ^a	Randomization/ start of IMP						To Y	'ear 2 (M24) [/])									From M27 to EOS	Only for participants who prematurely discontinue IMP	For all participants	Only for participants who completed treatment EOS but do not enter LTS ^C
Visit (a window of ±7 days is allowed for all visits after D1)	D-28 to D-1	D1	M0.5 (W2) M0.75 (W3)	M1(W4) ^d	M1.25 (W5) M1.5 (W6) M1.75 (W7)	M2 (W8) ^d	M2.25 (W9) M2.5 (W10) M2.75 (W11)	М3	M4, M5 ^d	M6	M7 M8	М9	M10 M11	M12	M15	M18	M21	M24	Quarterly visits (M27, M30, M33, M36, M39, M42, M45, M48)	Semi- annual visits (M30, M36, M42, M48)	pEOT ^e	EOS "Common study end date" visit ^f	Follow-up visit (4 weeks)
Visit Number	V1	V2		V3		V4		V5	V6, V7	V8		V9		V10	V11	V12	V13	V14	V15, V16, V17, V18, V19, V20, V21, V22	V16, V18, V20, V22	pEOT ^e	EOS	FUV
Study treatment administration																							
IMP dispensation		Х						Х		Х		Х		Х	Х	Х	Х	Х	Х	Х			
IMP Compliance								Х		Х		Х		Х	Х	Х	х	Х	Х	Х	Xe	Х	
Paper diary dispensation/collection		х						Х		Х		х		х	Х	х	Х	Х	х	х	Х	х	
Safety ^y																							
Physical examination ^h and vital signs	х	Х						Х		Х		х		х	Х	х	Х	Х	Х	х	х	Х	х
Height	Х																						
Body weight	Х	Х						Х		Х				Х		Х		Х		Х	Х	Х	Х

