Procedure	Screening ^a	Randomization/ start of IMP						To Y	ear 2 ((M24) ^k)									From M27 to EOS ^D	Only for participants who prematurely discontinue IMP	For all participants	Only for participants who completed treatment EOS but do not enter LTS ^C
Visit (a window of ±7 days is allowed for all visits after D1)	D-28 to D-1	D1	M0.5 (W2) M0.75 (W3)	M1(W4) ^d	M1.25 (W5) M1.5 (W6) M1.75 (W7)	M2 (W8) ^d	M2.25 (W9) M2.5 (W10) M2.75 (W11)	МЗ	M4, M5 ^d	M6	M7 M8	М9	M10 M11	M12	M15	M18	M21	M24	Quarterly visits (M27, M30, M33, M36, M39, M42, M45, M45, M48)	Semi- annual visits (M30, M36, M42, M48)	pEOT ^e	EOS "Common study end date" visit ^f	Follow-up visit (4 weeks)
Visit Number	V1	V2		V3		V4		V5	V6, V7	V8		V9		V10	V11	V12	V13	V14	V15, V16, V17, V18, V19, V20, V21, V22	V16, V18, V20, V22	pEOT ^e	EOS	FUV
Serology tests for hepatitis B and C	х																						
HIV and other infectious diseases, if required locally	х																						
TB/QuantiFERON® TB Gold test or equivalent ⁱ	х																						
Body temperature	Х	Х						Х		Х		Х		Х	Х	Х	Х	Х	Х	Х	Х	Х	Х
12-lead ECG ^j	Х							Х		Х		Х		Х				Х		yearly	Х	Х	
Hematology, biochemistry ^k	х	χz		Х		Х		Х	х	х		x		x	х	Х	х	х	х	х	Х	Х	х

Procedure	Screening ^a	Randomization/ start of IMP						To Y	ear 2 ((M24))									From M27 to EOS ^D	Only for participants who prematurely discontinue IMP	For all participants	Only for participants who completed treatment EOS but do not enter LTS ^C
Visit (a window of ±7 days is allowed for all visits after D1)	D-28 to D-1	D1	M0.5 (W2) M0.75 (W3)	M1(W4) ^d	M1.25 (W5) M1.5 (W6) M1.75 (W7)	M2 (W8) ^d	M2.25 (W9) M2.5 (W10) M2.75 (W11)		M4, M5 ^d	M6	M7 M8	М9	M10 M11	M12	M15	M18	M21	M24	Quarterly visits (M27, M30, M33, M36, M39, M42, M45, M45, M48)	Semi- annual visits (M30, M36, M42, M48)	pEOT ^e	EOS "Common study end date" visit ^f	Follow-up visit (4 weeks)
Visit Number	V1	V2		V3		V4		V5	V6, V7	V8		V9		V10	V11	V12	V13	V14	V15, V16, V17, V18, V19, V20, V21, V22	V16, V18, V20, V22	pEOT ^e	EOS	FUV
Liver function tests [/]			Х		Х		Х				Х		Х										
Iron panel (serum): iron, ferritin, transferrin saturation,TIBC; to be repeated during the study if needed	x																						
Coagulation: PT/INR, aPTT (to be repeated during the study, if needed)	x																						
Urinalysis	Х							Х						Х		Х		Х		Х	Х	Х	
Pregnancy test (if applicable) ^m	х	Х						Х		Х		х		х	х	Х	Х	Х	Х	Х	Х	х	Х

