a Screening period can range from D-28 to D-1; Randomization visit can be performed only once IMPs are available at site. The interval between screening and randomization visits can range from 11 days (minimum) to 28 days (maximum). However, if required, the randomization visit can be performed earlier than 11 days upon IMP receipt at the site, assuming the participant is eligible for randomization. In case of any delay to screening (MRI rescheduling, lab retests, etc), an additional period of up to 2 weeks is allowed.

b From D1 to EOS, unscheduled visits may be performed at any time by the Investigator (eg, for evaluation of an adverse event). Assessments may be done on as needed basis to evaluate the participant in accordance with the Investigator's best judgement and in-line with the study protocol. At a minimum, a physical examination should be performed, and body temperature and vital signs should be measured.

Amended Clinical Trial Protocol 12	
SAR442168-EFC16645 - tolebrutinib	

- c At the EOS, the participants who have completed treatment with IMP (double blind or open label if meeting CDP) may be offered participation in LTS study. Follow-up visit assessment only performed for those participants who completed treatment and are not willing to take part in the LTS study. For other situations where a follow-up visit is needed, please see Section 7.1 and the Study Manual.
- *d* These visits may be done as home health visits (where applicable) or onsite visits (it is preferable that tests are performed at the central laboratory). In any situations where this is not possible (to be documented in source documents), the tests for these visits may be performed at a local laboratory.
- e If a participant prematurely permanently discontinues treatment with IMP, the participant will undergo pEOT visit as soon as possible. A PK sample should also be collected if the pEOT visit can be scheduled within a maximum 24 hours after the last IMP dose. Participants will then be asked to continue with the study visits as scheduled until the common EOS Visit is reached. During these visits, all study procedures/assessments will be performed except IMP administration and blood sampling for PK and biomarkers (NfL, Chi3L1, and Ig levels). MRI scans for these participants will only be performed annually (using the next annual visit as the starting point). Additional information is provided in the Study Manual.

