- f For participants continuing in the study, the common EOS visit will be done when the prespecified number of events for 6-month CDP is expected to be reached. The timing and window of this visit will be communicated to sites.
- *g* Any disease-modifying therapy for MS taken at any time prior to signing the informed consent needs to be reported in the eCRF; other prior medications will be reported for the period of 6 months prior to signing the ICF.
- *h* Complete physical examination due at screening, baseline, yearly (M12, M24, M36, M48) and at EOS; brief physical examination is sufficient for the rest of the visits (complete and brief physical examinations will include neurological examination and collection of the following vital signs: arterial blood pressure, heart rate, temperature).
- *i* To be performed at screening for all participants. Tuberculosis examination will be repeated based on clinical judgment, borderline results, or clinical suspicion of TB infection. For further details, refer to E 01. Screening tests for TB are described in Appendix 2 (Section 10.2).
- *j* ECG and 30 second rhythm strips will be obtained locally.
- k Hematology (platelet count, RBC count, hemoglobin, hematocrit, MCV, MCH, reticulocytes, WBC count with differential: neutrophils, lymphocytes, eosinophils, basophils). Biochemistry (blood urea nitrogen [BUN], creatinine, glucose, sodium, potassium, bicarbonate, calcium, liver function tests [AST, ALT, ALP, albumin, total and direct bilirubin], total protein; creatine phosphokinase. Lipase will be tested at the Screening Visit, then quarterly. Monthly visits (M1, M2, M4, and M5) will include hematology and full liver panel only. Additional safety assessments can be performed if required by local regulations. Such testing shall be performed at local laboratories.

Note: a one-time retest at screening may be performed if laboratory test abnormality is considered temporary. Additional safety assessments can be performed if required by local regulations; such testing shall be performed locally whenever possible. Additional visits may be added if required by local regulations.

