#### Analyses according to PCSA

Potentially clinically significant abnormality (PCSA) analyses will be performed based on the PCSA list currently in effect at Sanofi at the time of the database lock. For parameters for which no PCSA criteria are defined, similar analyses will be done using the normal range.

Analyses according to PCSA (normal range) will be performed based on the worst value during the DB treatment-emergent period and OL period, using all measurements (either local or central, either scheduled, nonscheduled or repeated).

For laboratory variables, vital signs, and ECG variables above, the incidence of participants with at least one PCSA during the DB treatment-emergent period and OL period will be summarized respectively regardless of the baseline level and according to the following baseline status categories:

- Normal/missing
- Abnormal according to PCSA (normal range) criterion or criteria

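### Creatinine clearance is derived from same-visit weight with no fallback, so it cannot be derived at 7 of the 16 quarterly creatinine visits through Month 48

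*SAP*

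**What the plan says.** SAP section 3.6.3.1 lists creatinine, creatinine clearance and blood urea nitrogen as the renal variables. Clearance is calculated, not measured: "Creatinine clearance will be derived with the equation of Cockcroft and Gault using weight assessed at the same visit as creatinine." No other weight source is named.

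The SAP plans two uses of every laboratory variable on that list:

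- **By-visit summaries.** Results and changes from baseline are described in each analysis window, from central laboratory values, and mean changes are plotted over time. Under SAP section 5.4, a parameter with no measurement in a window is missing for that visit.
- **PCSA analysis.** Incidence is based on the worst value in the double-blind and open-label periods, "using all measurements (either local or central, either scheduled, nonscheduled or repeated").

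In protocol section 1.3, the row "Hematology, biochemistry" is marked at every quarterly visit, and footnote k puts creatinine in that panel: "Biochemistry (blood urea nitrogen [BUN], creatinine, glucose, sodium, potassium, bicarbonate, calcium". Body weight has its own row with fewer marks. For unscheduled visits, footnote b says: "At a minimum, a physical examination should be performed, and body temperature and vital signs should be measured."

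**The concern.** A clearance value needs a creatinine and a weight. If the weight must come from the same visit, clearance exists only where both were taken, and the schedule collects weight less often than creatinine. Measured creatinine values would then yield no clearance even though the participant had been weighed a few months earlier.

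Two outputs are affected. The clearance profile over time has no values at alternate quarterly visits from M9. The worst-value PCSA analysis, meant to use every available sample, would leave out clearance for samples without a weight. Those include follow-up samples: protocol section 8.2.4 asks for clinically significant abnormal laboratory values to be repeated, and nothing requires a weight with the repeat. The protocol treats clearance as informative: section 8.5 includes a clearance decrease of more than 50% in its description of a creatinine event.

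**Working it through.** The plan states no figure on this point, so the check is a count of the schedule followed by a short argument about direction.

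**Step 1. Visits with creatinine.** The biochemistry row is marked at M3, M6, M9, M12, M15, M18, M21 and M24 (8 visits), and again for "Quarterly visits (M27, M30, M33, M36, M39, M42, M45, M48") (8 visits). Footnote k removes the early monthly visits: "Monthly visits (M1, M2, M4, and M5) will include hematology and full liver panel only." Total: 8 + 8 = 16.

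**Step 2. Visits with weight.** The body weight row is marked at M3, M6, M12, M18 and M24 (5 visits) and in the semi-annual column, M30, M36, M42 and M48 (4 visits). It is blank at M9, M15, M21 and in the quarterly column. Total: 5 + 4 = 9. Screening, Day 1, premature end of treatment, end of study and follow-up have both measurements.

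**Step 3. Difference.** 16 − 9 = 7 visits: M9, M15, M21, M27, M33, M39 and M45. The share depends on follow-up:

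| Followed to | Creatinine visits | Without weight | Share |
|---|---|---|---|
| M24 | 8 | 3 | 37.5% |
| M30 | 10 | 4 | 40% |
| M36 | 12 | 5 | 41.7% |
| M48 | 16 | 7 | 43.75% |

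**Step 4. Cross-check.** SAP Table 8 has a biochemistry window at each of the seven visits and an empty weight cell at each. Its wide weight windows (days 127 to 252 for M6, for example) allocate weights to by-visit weight summaries; they do not turn an M6 weight into one taken at the M9 visit.

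**Step 5. Could another procedure supply the weight?** Footnote h lists vital signs as blood pressure, heart rate and temperature. Protocol section 8.2.1 puts weight in the complete physical examination, which footnote h schedules at screening, baseline, yearly and end of study, and leaves it out of the brief one. So nothing required at the seven visits, or at an unscheduled visit, guarantees a weight.

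**Step 6. Direction of the PCSA effect.** For low clearance the worst value is the minimum. If S is the set of a participant's creatinine samples and S′ the subset with a same-visit weight, then min over S′ ≥ min over S. For any threshold, a participant below it on S′ is also below it on S, but not always the reverse. The number counted can therefore stay the same or fall, and cannot rise.

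**Step 7. Age of a carried-forward weight.** At each of the seven visits the previous scheduled weight is one quarter earlier (M6 for M9, M12 for M15, and so on to M42 for M45): about 3 months. Scheduled weights are at most 6 months apart, so an unscheduled sample would use a weight up to about 6 months old if none was missed. I assume the usual form of the equation, in which clearance is proportional to weight (the SAP does not print it). A 5% weight change since the last weighing then gives an error of about 5% in clearance.

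**The case against.** The strongest reply is that renal safety does not depend on this variable. Serum creatinine and BUN need no weight. They are summarised at every biochemistry window and enter the worst-value PCSA analysis from every sample. Creatinine increase also has its own algorithm in protocol Appendix 6, and clinically significant values are reportable as adverse events. All of this stands. A reader might infer that a renal signal between semi-annual visits, or on an unscheduled draw, would go uncounted. The documents do not support that; only the derived clearance is lost.

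A second reply concerns unscheduled samples. Footnote b sets a minimum and allows further assessments as needed; a complete examination includes a weight; and the SAP itself lists weight among its vital signs variables. A local sample at a visit with a weight is usable. So it would be too strong to infer that every unscheduled or local creatinine loses its clearance. Nor are unscheduled draws necessarily renal in origin: the ALT work-up in Appendix 6 also calls for serum creatinine. What stands is that no weight is required there, so availability is left to chance.

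Third, the SAP does not say that clearance is derived only from same-visit weight or is otherwise set to missing, so a programmer might adopt a fallback. That is fair, but any fallback would depart from the one rule stated, and the SAP would not record which was used.

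Fourth, a sparser profile is ordinary for a descriptive variable: Table 8 has semi-annual weight and yearly ECG windows in later follow-up. This weakens the complaint about the time profile but does not answer the conflict with the all-measurements PCSA rule.

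**Conclusion.** The point holds as a minor, cheap improvement. Following SAP section 3.6.3.1 as written, creatinine clearance cannot be derived at 7 of 16 quarterly creatinine visits through M48, or at any unscheduled or repeat sample without a weight. That conflicts with the SAP's own by-visit and worst-value PCSA plans.

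The 44% is the share at full follow-up to M48; the protocol expects a mean treatment duration of 33 to 36 months, and the M36 share is about 42%. The count rests on the scheduled assessments and assumes no extra weights are taken.

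A reader might infer a material downward bias in the PCSA incidence, or a distortion between arms. The direction of the first is certain only in the weak sense of Step 6. Its size cannot be computed: the sponsor's PCSA list is not in the documents, nor is the number of participants whose clearance would cross a threshold only at a sample without a weight. Nothing in the documents points to a difference between arms. The safety analyses are descriptive with no testing, and no efficacy result depends on this variable.

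**What to change.** Amend SAP section 3.6.3.1 so that creatinine clearance uses the weight from the same visit or, if there is none, the last available weight on or before the creatinine sampling date. State that this applies to scheduled, unscheduled, local and repeat samples, in both the double-blind and open-label periods. The restriction of by-visit summaries to central values can stay.

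The cost is one sentence in the SAP and a line of programming, with no new data. The downside is a weight about 3 months old at the seven scheduled visits and up to about 6 months old at some unscheduled samples, in place of no clearance value. Fixing the rule before unblinding also avoids a programming choice made with the results in view.

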#### **Quantitative analyses**

For all laboratory variables, vital signs, and ECG variables above, descriptive statistics for results and changes from baseline will be provided for each analysis visit window during the DB treatment period and OL period respectively. These analyses will be performed using central measurements only for laboratory variables.

For each laboratory parameter, vital signs parameter and ECG parameter, mean changes from baseline with the corresponding SE will be plotted over time.

#### Analyses according to PCSA

Potentially clinically significant abnormality (PCSA) analyses will be performed based on the PCSA list currently in effect at Sanofi at the time of the database lock. For parameters for which no PCSA criteria are defined, similar analyses will be done using the normal range.

Analyses according to PCSA (normal range) will be performed based on the worst value during the DB treatment-emergent period and OL period, using all measurements (either local or central, either scheduled, nonscheduled or repeated).

For laboratory variables, vital signs, and ECG variables above, the incidence of participants with at least one PCSA during the DB treatment-emergent period and OL period will be summarized respectively regardless of the baseline level and according to the following baseline status categories:

- Normal/missing
- Abnormal according to PCSA (normal range) criterion or criteria

#### Additional analyses for drug-induced liver injury

The following additional analyses will be performed for drug-induced liver injury:

- Time to onset of the initial ALT or AST elevation (>3 x ULN) and total bilirubin elevation (>2 x ULN) during the treatment-emergent period will be analyzed using the KM method.
- The KM method will also be used to analyze time to onset of the following initial elevation ALT >3 x ULN, ALT >5 x ULN, ALT >8 x ULN, ALT >10 x ULN, AST >3 x ULN, AST >5 x ULN, AST >8 x ULN, AST >10 x ULN, total bilirubin >2 x ULN during the treatment-emergent period, respectively.
- A graph of the distribution of peak values of ALT versus peak values of total bilirubin during the treatment-emergent period will be provided.
- For each liver function test (eg, ALT), participants having experienced a PCSA (eg, ALT >5 x ULN) will be summarized using the following categories: Returned to baseline PCSA status (or returned to value ≤ULN in case of missing baseline) before last IMP dose, Returned to baseline PCSA status after last IMP dose, Never returned to baseline PCSA status, No assessment after elevation. This summary will be performed by categories of elevation ALT >3, >5, >10, >20 x ULN.

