In conclusion, considering the mechanism of action of SAR442168, the lack of data on the COVID-19 course in MS patients receiving DMTs, the safety monitoring and mitigation measures already in place, and the favorable benefit-risk profile observed in the completed Phase 2b study in participants with RMS, the Sponsor maintains that the trial can be initiated and conducted as planned.

Overall benefit: risk conclusion

No safety or tolerability concerns have been identified in the completed Phase 1 studies in healthy participants or the Phase 2b trial (DRI15928) in participants with RMS. In addition, the positive Phase 2b primary endpoint results support the potential for clinical efficacy.

Drug-induced liver injury, including severe DILI (risk of liver transplantation or death) as an identified risk, has been identified in the ongoing Phase 3 trials. The reported events occurred in Months 1 to 3 after the start of the IMP. Exclusion criteria and monitoring frequency have been updated in all actively recruiting protocols.

The potential risks associated with SAR442168 are well defined and appropriate safety monitoring measures and risk mitigation strategies are in place. The overall benefit/risk balance is acceptable for further clinical development of SAR442168.

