6.6.1 Open-label treatment

If a participant achieves the primary endpoint (6-month CDP), they may, in conjunction with the Treating Investigator, choose to receive one of the following:

- 1. To switch to open-label SAR442168 treatment; OR
- 2. To switch to a non-study treatment approved for NRSPMS in their respective country. In this case, the participant will permanently discontinue the IMP and will be encouraged to remain in the study for planned clinical visits (see Section 7.1.1) until common study end.

In case the participant switches to open-label SAR442168 treatment, he/she will need to be monitored for liver function tests after the first open-label dose at Weeks 2, 3, 4, 5, 6, 7, 8, 9, 10, 11, and 12, and then monthly for the next 9 months. After that, the schedule visits timepoints per SoA will be resumed (ie, every 3 months), until the common study end. Whenever a timepoint will coincide with a scheduled visit as per SoA (Section 1.3), the full scheduled visit assessments will be performed instead of the liver monitoring testing alone.

For participants achieving 6-month CDP, the Investigator must ensure that the participant does not meet any of the following criteria prior to the switch to open-label SAR442168 treatment:

• Current alcohol intake >2 drinks per day for men and >1 drink per day for women (1 drink = approximately 14 grams of alcohol = 350 mL beer = 140 mL wine = 40 mL of spirits).

- Acute liver disease, cirrhosis, chronic liver disease (unless considered stable for >6 months).
- Confirmed ALT >1.5 × ULN OR AST >1.5 × ULN OR ALP >2 × ULN (unless caused by non-liver-related disorder or explained by a stable chronic liver disorder) OR total bilirubin >1.5 × ULN (unless due to Gilbert syndrome or non-liver-related disorder).

Liver function tests will be performed for all participants prior to the start of open-label treatment.

Should the participant and Investigator opt for the provision of open-label medicine, they will remain blinded to the original treatment assignment.

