#### **Observation** period

The observation periods for safety will be divided into 4 epochs:

- The screening (pre-treatment) period is defined as the period from the signed informed consent date up to first administration of the study intervention.
- The **treatment period** (ie, treatment-emergent (TE) period) is defined as the period from the first administration of study intervention to
  - The earlier of last administration of the study intervention + 10 days or first IMP in the LTS study for participants not receiving tolebrutinib OL treatment,
  - The first administration of tolebrutinib OL treatment for participants switching to OL therapy

- The **OL period** (ie, OL TE period), applicable only for participants switching to tolebrutinib OL treatment, is defined as the time from first administration of tolebrutinib OL treatment to the earlier of last administration of OL treatment + 10 days or first IMP in the LTS study
- The **post-treatment period**, if applicable, is defined as the period from the end of treatment period (or end of OL period, if applicable) to the participant's final post-treatment study contact date.

Summaries of OL period data will be presented by original randomized treatment group and overall.

The on-study period is defined as the time from randomization until the end of the study defined as the last scheduled visit for those who completed the study and the end-of-study date collected on electronic case report form (e-CRF) page "Completion of End of Study" for those who did not complete the study. If death is the end-of-study reason, date of death will be used.

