#### Table 8 - Analysis window definition of safety variables

Note: Analysis windows in open-label period can follow the same rule except that the first open-label dose date is Day 1 in that period

	Taurat	Plasm samp (NfL), serum	na les n	0		Lymphoc	yte	Diacede		
AVISIT	Target Day	samp (Chi3l	les L1)	(lq levels)	mpies	flow cyto	flow cvtometrv		archiving	
		Start Day	Énd Day	Start Day	End Day	Start Day	End Day	Start Day	End Day	
Screening	-1							-40	-1	
Day 1	1	1	1	1	1	1	1			
Month 1	28									
Month 2	56									
Month 3	84	2	126							
Month 4	112									
Month 5	140									
Month 6	168	127	252	2	252					
Month 9	252									
Month 12	336	253	504	253	504					
Month 15	420									
Month 18	504									
Month 21	588									
Month 24	672	505	840	505	840					
Month 27	756									
Month 30	840									
Month 33	924									
Month 36	1008	841	1176	841	1176					
Month 39	1092									
Month 42	1176									
Month 45	1260									
Month 48	1344	1177	1386	1177	1386					
		Start Day: last visit window upper limit + 1; End Day: EOS visit date								
EOS		Nomina	ıl visit (9	000)						
		Start Da	ay: date	of discontinuat	ion + 1;					
		End Day: start of the next scheduled visit window								
pEOT		Map to the closest scheduled visit								

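### The liver displays that pair ALT with bilirubin stop at the first open-label dose and so omit placebo switchers' first months on tolebrutinib (optional; descriptive safety only)

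*SAP*

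**What the plan says.** SAP 3.6.3.1 lists four additional DILI analyses. The first is a joint analysis of ALT or AST above 3 x ULN with bilirubin: "total bilirubin elevation (>2 x ULN) during the treatment-emergent period will be analyzed using the KM method". The second gives Kaplan-Meier curves for single ALT, AST and bilirubin thresholds, in the same period. The third is the peak plot: "A graph of the distribution of peak values of ALT versus peak values of total bilirubin during the treatment-emergent period will be provided". The fourth, on whether liver abnormalities resolve, names no period.

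SAP 3.1 (Observation period) defines when the treatment period ends. For switchers the end point is: "The first administration of tolebrutinib OL treatment for participants switching to OL therapy". A separate open-label period starts at that dose. The SAP also says how open-label data are shown: "Summaries of OL period data will be presented by original randomized treatment group and overall".

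The laboratory abnormality (PCSA) analyses name both periods: "the incidence of participants with at least one PCSA during the DB treatment-emergent period and OL period will be summarized respectively".

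Protocol 2.3 names DILI, including severe DILI, as an identified risk and gives its timing: "The reported events occurred in Months 1 to 3 after the start of the IMP". Protocol 6.6.1 restarts intensive testing at the switch: "he/she will need to be monitored for liver function tests after the first open-label dose". Tests are due at Weeks 2 to 12 and then monthly for nine months.

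**The concern.** A placebo participant who reaches 6-month confirmed progression and takes open-label tolebrutinib is exposed to the drug for the first time at the switch. The liver risk window opens then, and the protocol collects near-weekly liver tests to cover it. The three displays close on the same day. A participant who developed raised ALT together with raised bilirubin two months later would not appear on the peak plot or in the joint Kaplan-Meier analysis. A reader using those displays to judge the drug's main identified risk would see only part of the first exposures that the trial generated.

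**Working it through.** **Is the exclusion real?** The SAP treats the treatment-emergent and open-label periods as distinct. It names both where it wants both: by-window laboratory statistics, PCSA incidence, suicidality and deaths. The first three DILI bullets name only the treatment-emergent period. On the SAP's own definitions, open-label data are outside them.

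**Does another open-label output pair ALT with bilirubin?** None does as listed. Adverse event summaries work by term. By-window statistics and PCSA summaries are listed variable by variable. The box and shift plots in SAP Appendix 5 also take ALT, AST, ALP and bilirubin one at a time. The sponsor's PCSA list is not supplied and could hold a joint criterion.

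**How many participants?** Inputs from SAP section 4: 288 events, 2:1 allocation, 30% risk reduction (taken as HR 0.70), 2-year placebo event rate 23.6%, 10% annual discontinuation, 24-month enrolment (taken as uniform) and 24-month minimum follow-up. The alternative is N = 1100 with about 30 months' minimum follow-up.

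The plan's own figure first. With 288 events, sqrt(288 x 2/3 x 1/3) x |ln 0.70| - 1.96 = 8 x 0.3567 - 1.96 = 0.893, which is 81.4% power against the stated 80%. It reproduces.

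Hazards per month:
- Placebo: -ln(1 - 0.236)/24 = 0.01122
- Tolebrutinib: 0.70 x 0.01122 = 0.00785
- Dropout d: -ln(0.9)/12 = 0.00878

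P(event by t) = lambda/(lambda + d) x (1 - exp(-(lambda + d)t)), averaged over follow-up of 24 to 48 months (N = 1290) or 30 to 54 months (N = 1100).

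| | N = 1290 | N = 1100 |
|---|---|---|
| Expected placebo events | 122.6 | 116.0 |
| Expected tolebrutinib events | 181.4 | 172.9 |
| Placebo share | 0.403 | 0.402 |
| Share x 288 | 116.2 | 115.7 |
| Fraction with onset at least 168 days before study end and no dropout in those 168 days | 0.845 | 0.867 |
| Placebo participants confirmed while in study | 98.2 | 100.2 |
| As share of all first exposures | 98.2/(98.2 + 860) = 10.2% | 100.2/(100.2 + 733) = 12.0% |
| Also with 84 more days in study | 89.2 | 92.6 |

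The count depends somewhat on the rule. A cruder count, not scaled to 288 events and asking only for onset six months before study end, gives about 92 to 108 across the two sample sizes and study lengths of 48 to 54 months. With HR = 1 the in-study figures are 81 and 83.

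**How many liver cases?** The documents give neither the proportion who switch nor a joint-case risk, so both are assumptions.
- A quarter switch: 98.2/4 = 24.5 and 100.2/4 = 25.1, about 25. At 0.5%, 25 x 0.005 = 0.12 cases.
- All switch: about 100. At 1%, 100 x 0.01 = 1.0 case.
- For comparison, among those randomized to tolebrutinib: 733 x 0.005 = 3.7 to 860 x 0.01 = 8.6 cases.

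**The case against.** The strongest reply is that the three displays use the right period for their purpose. Ending at the switch preserves the randomized comparison, because everyone in the open-label period takes tolebrutinib. That stands, and it is why the double-blind displays should not change.

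A reader might infer that open-label liver cases are lost. The documents do not support this. Protocol Appendix 2 (Table 5, footnote a) makes ALT above 3 x ULN with bilirubin at least 2 x ULN (more than 35% direct) an SAE. SAP 3.6.2 lists SAEs from randomized participants with no period limit, so each open-label case meeting that criterion is listed individually. Open-label adverse event summaries, open-label PCSA incidence and review by the independent hepatology committee add to this. With about one expected case or fewer, a listing may tell a reader more than a curve would.

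A reader might also infer a second gap, because INR is in no named SAP output although the same footnote makes ALT above 3 x ULN with INR above 1.5 an SAE. That does not hold as a defect. After screening, coagulation is tested only as needed, so a count would have no systematic denominator. Each such case is already reported and listed as an SAE.

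What remains is narrower: no planned open-label output, as listed, shows ALT and bilirubin together across participants.

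**Conclusion.** The point holds as a small, optional improvement to descriptive safety reporting. By the SAP's stated period definitions, placebo switchers' first exposure to tolebrutinib is outside the joint Kaplan-Meier analysis, the threshold curves and the peak ALT-bilirubin plot.

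About 98 to 100 placebo participants could be involved under the design assumptions. The true number of switchers should be lower: the protocol's liver and alcohol criteria, a choice of another therapy or of staying on double-blind drug, country-level supply, and earlier permanent discontinuation all reduce it. The expected number of joint cases omitted is about 0.1 to 1.0, resting on an assumed switch proportion (a quarter to all) and an assumed risk (0.5% to 1%). A joint criterion in the unseen PCSA list would already cover part of the gap. Case capture, safety oversight, type I error, power and the primary result are unaffected.

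**What to change.** Leave the double-blind displays as they are. Add open-label versions of the joint ALT/AST-bilirubin analysis and the peak ALT-bilirubin plot, by original randomized group. For the threshold curves, either add open-label versions or state that the open-label PCSA summaries cover them. Start the clock at the switch, a convention that the note to SAP Table 8 already uses for analysis windows: "the first open-label dose date is Day 1 in that period".

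The cost is a sentence or two in the SAP and a few extra outputs from data already collected. The new outputs have no randomized contrast and should be labelled as descriptive.
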